**Assessing Home Food Environment and Diabetes Self-management Among Adult Type 2
Diabetes Patients**

ClinicalTrials.gov identifier: NCT03039569

Date: June 1, 2018

Study Protocol

The current research project was approved by the University of Nebraska in Lincoln, Nebraska and the Methodist Health System in Omaha, Nebraska. Study participants were recruited from the Methodist Health System Center for Diabetes and Nutritional Health in Omaha, Nebraska. The center is an ambulatory outpatient clinic for treatment of patients with diabetes. Inclusion criteria were adults aged ≥ 30 years with Type 2 diabetes; self-reported hemoglobin A1C $>6.5\%$, having a cellular phone with the ability to receive text messages and English speaking.

A quasi experimental design was used in this pilot study due to timeframe restraints. Eligible participants who came into the clinic for outpatient diabetes management care were identified and approached. A survey regarding participants' demographics and, relevant risk factors for Type 2 diabetes was completed by all the participants (intervention and control group) at baseline.. The intervention group started approximately two months earlier than the control group. Participants in both the intervention and control groups received the usual care for Type 2 diabetes including an initial visit from either a Registered Dietitian or Certified Diabetes Educator and follow-up visits. The intervention group received three messages weekly (on Mondays, Wednesdays and Fridays) for 12 weeks based on topics regarding nutrition education and diabetes self-care information and skills. The messages were different each week during the first six weeks (Weeks 1 to 6) and repeated during the remaining weeks (Weeks 7 to 12). The messages consisted of strategies to increase fruits and vegetables and reduce high-fat and sugary foods intakes and to improve diabetes self-care skills, increasing physical activity, and increase awareness of CVD risk perception and knowledge (Table X). The text messages were derived from the topics and guidelines provided by the American Association of Diabetes Educator

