(AADE) including “Reducing Risks”, “Monitoring”, “Healthy Coping”, “Problem Solving”, “Taking Medication”, “Healthy Eating”, and “Exercise”. Each text message included the novel approach of including a link to a specific AADE7 topic and handout that allowed participants to open and retrieve the specific AADE7 information. Unidirectional text messages were sent by the project investigators to the participants in the intervention group via a computer-based text messaging program through a password protected computer which was only accessed by the investigators. Participants’ phone numbers used for text message intervention was kept private, and they were advised not to reply to the text message. If a participant had a medical concern about his/her diabetes, he/she was advised to contact his/her physician or call 911. The control group (usual care group) did not receive text messages. Participants in both the intervention (text messaging + usual care) and control group completed surveys regarding their awareness of CVD risk, diabetes self-care activities, dietary intake, and physical activity at baseline and at 12-week follow-up (conclusion of the intervention). Further, the participants in the intervention group completed a survey to evaluate their satisfaction with receiving text messaging for managing diabetes after the text messaging intervention was concluded. A \$25 gift card were offered to participants in both intervention and control groups.

Statistical Analysis

Primary analyses were based on participants in the intervention group or control group at the time of the initiation of the intervention (baseline) regardless of adherence status (intent-to-treat analysis). Baseline characteristics were calculated using descriptive statistics and compared between groups using t test for continuous variables and Chi-square analyses for categorical variables. Treatment effects were evaluated by assessing the differences in the outcome variables from baseline to the 12-week follow-up between participants in the intervention group and the

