control group using Proc Glimmix procedure. The model included the intercept, time effect (baseline and follow-up), and interactions between treatment groups (intervention and control groups) and the time effect (the absolute treatment effect). Least squares means were calculated for each time and treatment combination and the differences were calculated between treatments within each time point. Estimates of the absolute treatment/intervention effect were determined as follow: [(intervention group follow-up) – (intervention group baseline)] – [(control group follow-up) – (control group baseline)]. To provide perspective on the magnitude of the treatment/intervention effects, we also calculated proportional treatment/intervention effects, defined as (absolute treatment/intervention effect/intervention group baseline) × 100% (e.g., a proportional effect of 55% would mean a 55% increase in the intervention group relative to the control group). The analyses were repeated after the adjustment for unbalanced baseline characteristics (race/ethnicity, education) and the results did not change materially. SAS software (SAS Institute, Cary, NC) was used for analyses. All tests were 2-sided, and $P < 0.05$ was considered statistically significant.

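### The main effect estimate in this non-randomised pilot has no covariates, and its only adjusted repeat uses two characteristics picked because they looked unbalanced

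*Combined protocol and SAP*

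**What the plan says.** All references are to the combined protocol and SAP.

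- **Design (Study Protocol).** "A quasi experimental design was used in this pilot study due to timeframe restraints". Enrolment was also staggered: "The intervention group started approximately two months earlier than the control group".
- **Baseline data (Study Protocol).** "A survey regarding participants' demographics and, relevant risk factors for Type 2 diabetes was completed by all the participants (intervention and control group) at baseline". Its individual items are not listed. A1C appears only as a self-reported entry criterion.
- **Baseline comparison (Statistical Analysis).** Characteristics were "compared between groups using t test for continuous variables and Chi-square analyses for categorical variables". The only significance rule given is general: "All tests were 2-sided, and $P < 0.05$ was considered statistically significant".
- **Main model (Statistical Analysis).** The Glimmix model has an intercept, time, and group-by-time terms. The effect is the change in the intervention group minus the change in the control group. No covariate is listed.
- **Adjusted analysis (Statistical Analysis).** "The analyses were repeated after the adjustment for unbalanced baseline characteristics (race/ethnicity, education) and the results did not change materially".

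The section gives no sample size, no threshold for calling a characteristic unbalanced, and no list of confounders chosen for their relevance to the outcomes. It also does not say whether the two adjusters entered as main effects or with a time interaction.

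**The concern.** Without randomisation, the groups may differ systematically in ways that affect how much participants change. The plan's result rests on a model that takes no account of measured differences. Covariates enter only in a repeat, and only because they looked unbalanced.

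A baseline test measures the evidence for an imbalance, and that depends on sample size. It does not show whether the variable predicts 12-week change. In a small study it can pass over a real imbalance in a strong predictor and flag one in a variable that does not matter.

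At stake is bias in the reported effect, together with false reassurance from an adjusted repeat that examined two variables.

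**Working it through.** **Inputs.** From the documents: the difference-in-differences estimate and the two-sided 0.05 level. Assumed, because the documents are silent: 30 or 50 per arm; within-group SD of change equal to 1; confounders independent of one another, with imbalance d of 0.3 or 0.4 SD and correlation r with change of 0.25 or 0.3; no true effect. That *unbalanced* means P < 0.05 is inferred from the baseline tests and the general significance rule. The plan states no power or effect-size figure to reproduce.

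**1. What the estimate already removes.** If a covariate adds the same amount to the outcome at both visits, it drops out of each participant's change. Only a covariate related to change can bias the estimate.

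**2. Chance that a baseline t test flags a true imbalance** (noncentral t, noncentrality d × √(n/2)):

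| True imbalance | 30 per arm | 50 per arm |
|---|---|---|
| 0.3 SD | 21% | 32% |
| 0.4 SD | 33% | 51% |

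Flagging a 0.3 SD imbalance with 80% probability needs 175 per arm.

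**3. Bias of the unadjusted estimate.** Each confounder contributes r × d, in SDs of change. The standard error is √(2/n): 0.258 at 30 per arm and 0.200 at 50. Type I error follows from the noncentral t with noncentrality bias/SE.

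| Scenario | Bias | Type I error, 30 / 50 per arm |
|---|---|---|
| One: r = 0.25, d = 0.3 | 0.25 × 0.3 = 0.075 | 5.9% / 6.6% |
| One: r = 0.3, d = 0.4 | 0.3 × 0.4 = 0.12 | 7.4% / 9.1% |
| Four, same direction: r = 0.25, d = 0.3 | 4 × 0.075 = 0.30 | 21% / 32% |
| Four, two reversed | 0.15 − 0.15 = 0 | about 5% / 5% |

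The four-confounder case assumes that together they explain 4 × 0.25² = 25% of the variance of change.

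**4. Adjusting only for flagged variables** (simulation, no true effect):

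- One confounder (r = 0.3, d = 0.4): bias falls from 0.12 to about 0.05 at 30 per arm and 0.04 at 50. Type I error is about 5%.
- Four in the same direction: bias falls from 0.30 to about 0.17 and 0.13. Type I error is about 9% to 10%.
- Four with two reversed: bias is near 0 and type I error 4% to 5%.

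Adjusting for all four on the change, whatever their P values, gives bias near 0 and type I error of 5% to 6%.

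**5. How the covariate enters.** In one simulated complete data set, adding the covariate as a main effect left the difference in differences at 0.1198. Adding covariate by time moved it to 0.0139. If race/ethnicity and education entered as main effects only, an almost unchanged result would be expected whether or not they confound change.

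**The case against.** **The difference in differences is itself a control for confounding.** This stands. It removes every confounder with a constant additive effect, so a reader who infers that covariate adjustment is the only protection in this design goes too far. Confounding of change is what remains.

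**Screening does not in general inflate the false-positive rate.** This also stands. With one confounder, or with opposing ones, type I error under screening stays near 5%. It reaches 9% to 10% only when four confounders all push the same way, and there the unadjusted model does far worse. The larger error belongs to the unadjusted main analysis; screening is a partial repair.

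**The scenarios are chosen.** True: the documents give no sample size, imbalance or correlation, and small size is inferred from the word pilot. The figures show what could happen, not what did.

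**A1C.** A reader might infer that an entry A1C value was collected and left out. The documents do not support that: A1C is a self-reported eligibility threshold, and no section says that a value was recorded.

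**More adjusters can cost precision.** This stands for a long list. With one real confounder (r = 0.25, d = 0.3) and nine irrelevant adjusters, adjusting for all gives a standard error of 0.279 against 0.266 under screening at 30 per arm, and 0.202 against 0.197 at 50. Overall accuracy is then no better.

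**The results are already known.** The text is in the past tense, so promoting an adjusted model now is itself a choice informed by the data. That calls for a clear label and for showing both estimates.

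**Conclusion.** The point holds in a limited form. The main estimate is unadjusted in a non-randomised study, the adjusters were chosen by observed imbalance, and the statement of no material change covers two variables only.

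The principal harm is bias in the unadjusted estimate from factors related to 12-week change. Under the assumptions above it is about 0.08 to 0.12 SD for a single modest confounder, 0.30 SD when four act together, and near zero when they offset. Adjusting only for flagged variables leaves part of it in place.

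The documents do not show that the reported result is wrong, nor in which direction any bias runs. Covariates also cannot remove the effect of the roughly two-month gap between the groups' starts, because start period is tied to group.

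**What to change.** 1. Choose a short adjuster list on subject-matter grounds, whatever the baseline P values. Draw it from the baseline demographics (for example age, sex, race/ethnicity and education, where recorded) and the surveyed diabetes risk factors. Add A1C only if a value was recorded. Keep the list in proportion to the sample size.
2. Enter the adjusters so that they act on change, with covariate-by-time terms. State how race/ethnicity and education entered the existing repeat.
3. Report this as the main estimate, labelled post hoc, beside the unadjusted one.
4. Describe balance by standardised differences and stop using baseline tests to select covariates.
5. Limit the claim of no material change to the two variables tested, and state that adjustment cannot remove the offset in start dates.

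**Cost.** Revised wording and a few lines of code on survey data already collected. The price is a few degrees of freedom, possibly a small loss of precision if the adjusters are weak, and the post hoc label.
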